7.2 Video Modeling Intervention

The video modeling intervention consists of the first four BE SAFE The Movie Curriculum Lessons (https://besafethemovie.com/curriculum/). The BE SAFE The Movie Curriculum consists of video-based instruction on police officer interaction expectations and safety. These include Lesson 1: Laws Help us BE SAFE; 2: Law Enforcement Officers Help Us BE SAFE; 3: Uniforms and Safety Tools; 4: Stay Calm When You Meet the Police; Participants will be shown videos from lessons, and then complete additional engaging video-based activities and short movie scenarios to video model.

8 SAFETY MANAGEMENT

8.1 Clinical Adverse Events

Clinical adverse events (AEs) will be monitored throughout the study. The PI and the research team will work together to minimize minor adverse events. This will be accomplished through systematic assessment for adverse events through active clinical observation and post-session

questionnaires. If adverse events occur, we will solicit direct guidance and feedback from CHOP's IRB, and immediately implement safeguards to decrease or eliminate future risks. Minor AEs that are unrelated to study participation will be reported to CHOP's IRB and the NIH program officer in a quarterly report.

Safety research on Virtual Reality (VR) indicates that photosensitive seizures, headache, and vertigo are adverse events possibly related to VR use. Our study team will consider new onset seizure disorder, any seizure triggered during participation, and either headache or vertigo severe enough to result in an emergency room evaluation or hospitalization to be SAEs and respond accordingly.

8.2 Adverse Event Reporting

Since the study procedures are not greater than minimal risk, SAEs are not expected. If any unanticipated problems related to the research involving risks to subjects or others happen during the course of this study (including SAEs) they will be reported to the IRB in accordance with CHOP IRB SOP 408: Unanticipated Problems Involving Risks to Subjects. AEs that are not serious but that are notable and could involve risks to subjects will be summarized in narrative or other format and submitted to the IRB at the time of continuing review.

[name] (PI) will be responsible for handling SAEs and AEs that may occur during this study. Taking NIMH guidelines into account, we will implement rigorous protocols at each site (CHOP) to ensure that SAEs and AEs are rapidly reported to [name]. All SAEs will be reported to [name] within 24 hours. At CHOP, SAEs will be reported directly to [name] by study staff. [name] will notify CHOP's IRB and NIH program officer about SAEs within 72 hours.

9 STUDY ADMINISTRATION

9.1 Treatment Assignment Methods

9.1.1 Randomization

We will employ stratified random assignment using variables including developmental age and sex. Other participant variables that differ between our groups following this stratified randomized assignment will be accounted for statistically during our primary analyses.

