3.1.2 Cycle A – Laboratory-Based Efficacy Study

In the first year of the study, an efficacy study will be conducted at the Center for Autism Research. Subjects will be randomized to the VR intervention or to the video modeling control condition (with stratification, see *Study Procedure*). Subjects in each condition will undergo a baseline assessment of police interaction skills via a live role play with a study staff member and three sessions of their assigned intervention within an approximately six-week period. At the end of Visit 3, subjects' police interaction skills will be assessed via a live interaction with a police officer.

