3.3 Study Population

3.3.1 Inclusion Criteria

- 1) Males or females age 12 to 60 years
- 2) Documented ASD diagnosis
- 3) Verbal and overall IQ \geq 75 (Cycle A)/Verbal and overall IQ \geq 80 (Cycle B)
- 4) Informed consent (if adult) or parental/guardian permission (if child or adult with diminished capacity) and, if applicable, assent

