4.2 Characterization Visits

- Informed Consent, and assent if appropriate
- IQ testing (completed at first visit)
- ASD diagnostic testing (completed at any of the 3 intervention study visits in Cycle A only)
- Self-report measures
- Parent-report questionnaires
- Stratified randomization to either the VR intervention or to the video modeling control condition
- Medical or Research Record Review

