5.1.2 IQ testing

Cognitive function, including verbal and non-verbal intelligence, will be assessed using the Wechsler Abbreviated Scale of Intelligence, Second Edition (WASI-II; Wechsler & Hsiao-pin, 2011) or other equivalent IQ test. Subjects with a verbal and overall IQ greater than or equal to 75 (Cycle A), or 80 (Cycle B) will continue with the study.

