6.4 Sample Size and Power

This study will compare the PSM VR intervention to treatment-as-usual (TAU) in a total of 96 adolescents and adults with ASD, in two separate studies (i.e., n=48 per study). The most relevant study to date (Didehbani, Allen, Kandalaft, Krawczyk, & Chapman, 2016) included 30 7-16 year-olds with ASD in a pre/post virtual reality intervention to improve social cognitive skills. This study suggested a medium-to-large within-group effect of VR intervention on emotion recognition (Cohen's d = .63), but did not compare two interventions. Sensitivity analysis using G*Power indicated that intervention differences using our proposed sample size (N=48 per group) will be detected with a critical t of 1.99, and that we will be able to detect differences with effect sizes of Cohen's d = .74 or larger. Data will be behaviorally coded from video interactions and correct answers marked on knowledge tests. Scores will be summed, averaged, and examined for normality at the group level. Normally distributed data will be analyzed using parametric statistics (e.g., ANOVA, regression, Pearson correlation), and data that do not meet normality assumptions will either be transformed or will be analyzed using nonparametric statistical tests (e.g., Chi-square, Spearman correlation). Analyses will be corrected for comparisons. To compare PSM to BE SAFE, an Analysis of Variance (ANOVA) with Group (PSM VR Intervention, BE SAFE The Movie Video Modeling Intervention) as a Between-Subjects factor will be conducted for Live Interaction data. A separate ANOVA (or comparable statistical test) will be conducted for Questionnaire data. Relevant potential covariates include knowledge of police interactions at intake, sensory sensitivity scores, verbal abilities, and chronological age.

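### The factors used to stratify randomisation are not in the stated primary model, and one of them, developmental age, has no stated source, levels or adult rule

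*Combined protocol and SAP*

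**What the plan says.** Section 9.1.1 is the only place that names stratification factors: "We will employ stratified random assignment using variables including developmental age and sex". Its next sentence promises statistical adjustment for other participant variables that still differ between groups.

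For detail, section 3.1.2 sends the reader elsewhere: "Subjects will be randomized to the VR intervention or to the video modeling control condition (with stratification, see *Study Procedure". Section 3.1.3 uses the same pointer for Cycle B. The procedures in section 4.2 say only "Stratified randomization to either the VR intervention or to the video modeling control condition", which gives no factors or levels and names only the Cycle A arms.

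The eligible population is "Males or females age 12 to 60 years" (3.3.1), with an IQ floor: "Subjects with a verbal and overall IQ greater than or equal to 75 (Cycle A), or 80 (Cycle B) will continue with the study" (5.1.2). On the cognitive measure, 5.1.2 says "Cognitive function, including verbal and non-verbal intelligence, will be assessed using the Wechsler Abbreviated Scale of Intelligence, Second Edition", or an equivalent test. Section 4.2 times it as "IQ testing (completed at first visit"), and 6.3.2 places randomisation at Visit 1.

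On the analysis, section 6.4 specifies, for the Cycle A live interaction data, an ANOVA with Group as the between-subjects factor and names no other. It adds: "Relevant potential covariates include knowledge of police interactions at intake, sensory sensitivity scores, verbal abilities, and chronological age". Section 6.3.1 makes a baseline characteristic a covariate if it shows a statistically significant group difference. Section 5.1.5 says that demographic data enter as covariates when groups are not matched on critical features. For the Cycle B primary endpoint, 6.3.2 describes the comparison but gives no model.

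**The concern.** When randomisation is stratified, the analysis should normally carry the same factors. Stratification removes their contribution from the true variance of the treatment difference. A model that omits them leaves that contribution in the error term, so the standard error is too large, the test is conservative and the benefit of stratifying is partly thrown away. With about 48 evaluable subjects per cycle and ages from 12 to 60, that benefit is worth keeping.

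The covariate rules in the plan do not repair this. A rule triggered by a significant baseline difference is least likely to fire for a factor that stratification has balanced. A rule for other variables leaves the stratification factors out by its wording.

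A model can also include only factors that are defined. Developmental age appears once, without an instrument, derivation, number of levels or cut-points. Two statisticians given this protocol could build different randomisation lists and different strata for the analysis.

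**Working it through.** **1. Are the stratification factors in the analysis?**

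| Route into the model | Sex | Developmental age | Chronological age |
|---|---|---|---|
| ANOVA factors (6.4) | no | no | no |
| Potential covariates (6.4) | not named | not named | named, not committed |
| Significant baseline difference (6.3.1) | only if significant | only if significant | only if significant |
| Demographic data when groups are unmatched (5.1.5) | conditional | conditional at most | conditional |
| Other variables that differ (9.1.1) | excluded by wording | excluded by wording | only if it differs |

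No route commits either stratification factor to the model.

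**2. Are the strata reproducible?** The measures in 5.1 to 5.4 are an IQ test, ADOS-2, SCQ, AQ, a sensory profile, behaviour checklists, SRS-2, a demographic form and study-made police and feedback measures. None is said to yield a developmental age. ADOS-2 is done in Cycle A only and at any of three visits, so it cannot reliably feed assignment at Visit 1.

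Readings of the term differ. One possibility, which the documents do not propose, is a ratio score, IQ × age / 100. It gives 75 × 12 / 100 = 9.0 at age 12 with IQ 75, and 80 × 50 / 100 = 40 at age 50 with IQ 80. The second value is the same as for age 40 with IQ 100 (100 × 40 / 100 = 40). Another reading is simply adolescent versus adult. These produce different strata.

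**3. What does omission cost?** The plan gives no figure to reproduce. Inputs: 48 per cycle (3.2.2, 6.4) and 24 per arm, which assumes 1:1 allocation (6.4 also speaks of 48 per group; I follow the per-study figure). Residual degrees of freedom are 48 − 2 = 46. Let r be the correlation of the stratification factors, taken together, with the outcome. The documents do not give r, so I show a range. With balanced factors:

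- true SE / SE from the Group-only model = sqrt(1 − r²)
- actual size of a nominal 5% test ≈ P(|Z| > 1.96 / sqrt(1 − r²))
- detectable d with the factors in the model ≈ 0.83 × sqrt(1 − r²), where 0.83 is the effect detectable with 80% power by a two-sample t test at 24 per arm

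| r (assumed) | sqrt(1 − r²) | SE overstated by | Actual size | Detectable d, adjusted |
|---|---|---|---|---|
| 0.2 | 0.980 | 2% | 4.5% | 0.81 |
| 0.4 | 0.917 | 9% | 3.2% | 0.76 |
| 0.6 | 0.800 | 25% | 1.4% | 0.66 |

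A simulation of an unadjusted t test, with a two-level factor perfectly balanced at 24 per arm, gave sizes of 4.5%, 3.4% and 1.5%.

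**4. Would the significance rule catch an age difference?** The SD of the between-arm difference in a standardised covariate without stratification is sqrt(1/24 + 1/24) = 0.289. The critical t on 46 df is 2.013, so the rule fires only above 2.013 × 0.289 = 0.58 SD. A gap of 0.5 SD gives t = 0.5 / 0.289 = 1.73, p ≈ 0.09, and would go unadjusted.

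**5. Price of adjusting.** Sex and a two-level age factor use 2 df, leaving 44. Adding continuous chronological age uses 3, leaving 43. The critical t moves from 2.013 to 2.015 or 2.017.

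**The case against.** The fair defence has three parts.

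First, the plan does contemplate age adjustment. Section 6.4 lists chronological age and verbal abilities as relevant covariates, and 5.1.5, 6.3.1 and 9.1.1 all provide for adjustment. This stands in part: a sensible analyst could include age. But nothing commits to it, sex is not listed, and the triggers depend on observed imbalance.

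Second, a reader might infer that stratifying on developmental age is impossible, or meaningless for adults. The documents do not support that. IQ testing and randomisation both fall at the first visit, so IQ and chronological age could both be available at assignment and a score could be derived. The protocol describes its population as adolescents and adults throughout, so the term may mean developmental stage. Whether the concept suits adults is a psychometric question the documents do not settle. What is missing is a definition. Stratification by sex is unaffected.

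Third, a reader might infer that the wording leaves age unbalanced and biases the result. At 24 per arm, unstratified randomisation gives a mean-age gap above 0.5 SD about 8% of the time. That describes chance imbalance with no age stratification at all; it does not measure harm from this wording. Chance imbalance averages to zero over randomisations and is covered by the standard error, so it is not bias. If developmental age tracks chronological age, stratifying on it would balance much of age anyway. Nor do the documents say that staff would choose the stratum at their discretion.

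**Conclusion.** The point holds as an omission from the model together with a definition gap. The stratification factors in 9.1.1 are in neither the stated ANOVA nor any unconditional covariate rule, and developmental age cannot be reproduced as a stratum from the text.

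The size depends on how prognostic the factors are: from almost nothing at r = 0.2 to a material loss of precision at r = 0.6. These figures assume 24 per arm, balanced factors and an approximately linear model; r itself is assumed. The direction is conservative, so a positive result would not be undermined on this ground. It remains worth correcting because it costs almost nothing and removes a data-dependent choice of covariates. Replacing developmental age with chronological age is one option and is partly a matter of preference; defining whichever factor is used is not.

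**What to change.** - **9.1.1:** replace the open list with a closed list of factors and their levels, applied separately in each cycle and read from data available before randomisation. Use sex plus one age factor: either a chronological age band (for example 12–17 versus 18–60, following the adolescent/adult split already used for assent and questionnaires), or developmental age with its source measure, derivation, cut-points and rule for adults. If it uses the IQ test, state that the test is scored before assignment within Visit 1.
- **4.2:** repeat the factors and name the arms for both cycles, so that the pointers in 3.1.2 and 3.1.3 lead somewhere.
- **6.3.2 and 6.4:** prespecify the same factors, with chronological age as a covariate, in the primary model of each cycle regardless of observed imbalance.

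The cost is protocol wording, set-up of the randomisation list and two to three degrees of freedom out of about 46. No new measure is needed. If chronological age band replaces developmental age, any indirect balance on IQ is lost; verbal ability remains available as a covariate. Two age bands also leave age within 18–60 uncontrolled at randomisation, which is why continuous age belongs in the model too.

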9.1.2 Blinding

Study staff members and Police officers serving as confederates in the Baseline Assessment and Police Interaction Assessment and those that code the interactions will be blinded to intervention condition.

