3.1.3 Cycle B – Virtually-Based Efficacy Study

In the second year (after the completion of Cycle A), a virtually-based efficacy trial will be conducted by CHOP staff via videoconference. Subjects will be randomized to the VR intervention or to the treatment-as-usual condition (with stratification, see *Study Procedure*). Subjects in each condition will undergo a baseline assessment of police interaction skills via a novel pre-/post-intervention assessment and three sessions within an approximately six-week period. At the end of Visit 3, subjects' police interaction skills will be assessed. There will be an additional follow-up visit approximately 4 weeks post-training, for all participants, to readminister outcome measures, as an assessment of maintenance of learning.

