5.4.1.2 Cycle B

Before beginning the first VR or video modeling intervention session, all participants will complete a baseline novel remote assessment of police interactions skills. These interactions are designed to measure each participant's ability to interact with a virtual police officer prior to completing either intervention. This assessment will include coded video recordings of participants wearing the VR headset while engaging in a standardized experience. The behaviors of the participant inside the virtual environment will also be coded. The interaction is designed with guidance from law enforcement officers with particular experience working with individuals with intellectual and developmental disabilities. The live interaction will be video-recorded via a CHOP-approved, HIPPA compliant videoconference platform. These recordings will be coded for a set of behaviors that would encourage successful police interactions (i.e.: making appropriate eye contact, etc.)

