6 STATISTICAL CONSIDERATIONS

6.1 Primary Endpoints

The primary efficacy endpoints will be the change in post-treatment Live and Virtual Police Interaction Assessment Scores between the Virtual Reality Intervention and treatment-as-usual groups, and the change in scores between the Baseline Assessment and Virtual Police Interaction Assessment.

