6.2 Secondary Endpoints

Secondary endpoints will include the following:

- The changes in Police Interaction Knowledge Questionnaire Scores from Pre-Treatment to Post-Treatment for the Virtual Reality Intervention and BE SAFE Video-Based intervention or treatment-as-usual:
- The maintenance of learned skill improvements, indexed via the 4-week (Cycle B) Follow-Up administration of the Virtual Police Interaction Assessment.

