6.3.2 Efficacy Analysis

The primary analysis will be based on an intention to treat approach and will include all subjects randomized at Visit 1.

The primary efficacy endpoint will be the change in post-treatment Live Police Interaction Assessment Scores between the Virtual Reality Intervention and BE SAFE Video-Based intervention and the change in scores between the Baseline Assessment and Live Police Interaction Assessment. In the case of Cycle 2, the Baseline Assessment will be compared to the Virtual Police Interaction Assessment between the Virtual Reality Intervention and treatment-asusual groups. The study hypothesis is that participants randomly assigned to the Virtual Reality Intervention will perform better on the post-treatment Live or Virtual Police Interaction Assessment than will participants randomly assigned to the BE SAFE Video-Based intervention or treatment-as-usual condition.

The secondary endpoint will include changes in Police Interaction Knowledge Questionnaire Scores from Pre-Treatment to Post-Treatment for the Virtual Reality Intervention and BE SAFE Video-Based intervention or treatment-as-usual. The study hypothesis is that participants randomly assigned to the Virtual Reality Intervention will exhibit significantly greater improvement from Pre-Treatment to Post-Treatment on Police Interaction Knowledge Questionnaire than will participants randomly assigned to the BE SAFE Video-Based intervention condition or the treatment-as-usual condition. An additional Secondary endpoint is maintenance of learned skill improvements, indexed via the 4-week Follow-Up administration of the Virtual Police Interaction Assessment in Cycle B. The study hypothesis is that participants randomly assigned to the Virtual Reality Intervention will exhibit significantly greater Live Police Interaction Assessment Scores and skill improvement/maintenance 4-week follow-up than will participants randomly assigned to the treatment-as-usual condition.

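### Cycle B coders are masked to intervention condition, but masking to visit is not specified, so within-arm change from baseline is open to coder expectation

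*Combined protocol and SAP*

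**What the plan says.** Section 9.1.2 is the whole of the blinding text. On coders it says that "those that code the interactions will be blinded to intervention condition". It does not mention visit, date or scoring order. Section 5.5 (recording) and sections 9.2 and 9.3 (data management, confidentiality) do not mention them either; the subject identifiers there protect privacy and do not hide the time point.

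The Cycle B scores depend on those coders at every time point. For baseline, 5.4.1.2 says "This assessment will include coded video recordings of participants wearing the VR headset while engaging in a standardized experience". Section 5.4.2.2 has the Visit 3 and 4-week assessments coded from recordings of the participant in the headset and of behaviour inside the virtual scene. Section 3.1.3 describes a "baseline assessment of police interaction skills via a novel pre-/post-intervention assessment", so one instrument appears to serve before and after training.

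The endpoint text comes in two forms:

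- Section 6.1 gives an arm comparison first: "The primary efficacy endpoints will be the change in post-treatment Live and Virtual Police Interaction Assessment Scores between the Virtual Reality Intervention and treatment-as-usual groups". It then adds, as a further item, "the change in scores between the Baseline Assessment and Virtual Police Interaction Assessment", with no arm comparison in that clause. Section 6.2 lists maintenance as "indexed via the 4-week (Cycle B) Follow-Up administration of the Virtual Police Interaction Assessment", also without naming a comparison.
- Section 6.3.2 supplies the comparison for Cycle B (which it calls Cycle 2): "the Baseline Assessment will be compared to the Virtual Police Interaction Assessment between the Virtual Reality Intervention and" the treatment-as-usual arm. Its maintenance hypothesis is likewise comparative: "skill improvement/maintenance 4-week follow-up than will participants randomly assigned to the treatment-as-usual condition".

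**The concern.** Behaviours such as appropriate eye contact or orienting to the officer need judgement to score. A coder who knows that a recording was made after training may score it more generously than a baseline recording, even without knowing the arm. Arm masking does not prevent this.

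The damage depends on which comparison is reported. A shift common to both arms drops out of a difference between arms, but goes in full into a change from baseline within an arm. Because 6.1, read alone, lets that change stand as a primary result, a gain produced by coding could be presented as efficacy of the VR module.

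**Working it through.** **The plan's own figure.** The only numerical design figure is in section 6.4: critical t 1.99 and detectable d of 0.74 with 48 per group. With a two-sided 5% level (assumed), 48 per group gives 94 df, critical t 1.986, and d = 0.743 at 95% power, so it reproduces. It does not bear on coder masking. It matters here only because 6.4 also says 48 per study, which is 24 per arm if allocation is 1:1 (ratio not stated). I use 24.

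**Inputs**

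- n = 24 per arm: 48 / 2, from 6.4, assuming 1:1.
- Pre-post correlation r = 0.5 or 0.7: assumed.
- Coder inflation b = 0.1, 0.2 or 0.3 SD on post-training recordings: assumed; the documents give no basis for a value.
- No true change; two-sided 5% test.

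**Step 1: within one arm.** With unit SD at each time point, the SD of change is √(2(1−r)): 1.000 at r = 0.5 and √0.6 = 0.775 at r = 0.7. A paired t-test has 23 df and critical t 2.069. Its noncentrality under the coder shift is b√24 / √(2(1−r)). For b = 0.2 and r = 0.5 that is 0.2 × 4.899 / 1.000 = 0.98.

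| b (SD) | Noncentrality, r = 0.5 | False positive | Noncentrality, r = 0.7 | False positive |
|---|---|---|---|---|
| 0.1 | 0.49 | 7.6% | 0.63 | 9.3% |
| 0.2 | 0.98 | 15.6% | 1.26 | 22.8% |
| 0.3 | 1.47 | 29.1% | 1.90 | 44.4% |

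A simulation of 40,000 trials gave 15.6% and 29.2% (r = 0.5) and 23.0% and 44.3% (r = 0.7) for b = 0.2 and 0.3, and about 5% with b = 0. A weaker correlation of 0.3 gives 6.8%, 12.5% and 22.2%. A paired test on 48 subjects (both arms pooled) gives 27% to 42% at b = 0.2 and 53% to 75% at b = 0.3.

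**Step 2: between arms.** In the same simulation, with the same b added to every post-training score in both arms, the two-sample test of change or of post-training score rejected in 4.7% to 5.1% of trials at every b up to 0.5 SD. The mean arm difference was about 0. A shared shift cancels.

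**Step 3: what it would take to affect the arm comparison.** The shift would have to differ between arms. As an illustration only, a differential shift of 0.2 SD gives noncentrality (0.2 / SD of change) × √(24/2): 0.69 at r = 0.5 and 0.89 at r = 0.7. The false-positive rate for the arm difference in change is then about 10% and 14%. Nothing in the documents shows that such a difference would arise.

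**The case against.** The strongest reply is that Step 1 describes a test the efficacy section does not plan. Section 6.3.2 compares the arms in Cycle B, for the main result and for maintenance; the model named in 6.4 (for the Cycle A comparison) has group as a between-subjects factor; and no section specifies a paired test. Arm masking protects that comparison, and it is stated. This stands, and it limits the point to within-arm change. It does not dispose of it, because 6.1 is the endpoint definition and its wording still allows a within-arm gain to be reported as primary.

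Three stronger readings are tempting and not supported:

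- **That coders will know the visit.** The documents are silent; they do not say so. The point is that nothing prevents it.
- **That the treatment effect is biased.** A reader might argue that a coder who knows a recording is post-training can guess the arm from how easily the headset is used, since treatment-as-usual subjects meet the software only for assessments (5.3.2). This is possible but not shown. The cue is on the recording whatever its label, so visit masking would reduce it only in part. A ceiling on the scores could also leave a residue; that is not shown either.
- **That maintenance is inflated.** Visit 3 and 4-week recordings both follow training, and a coder might expect decay as readily as retention. The direction is unknown, and the rates above cover only baseline to post-training.

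It is also true that masking visits would not make within-arm change evidence of efficacy: practice on a repeated assessment and regression to the mean would remain. That is why the fix has a second part.

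**Conclusion.** The point holds for within-arm change in Cycle B. Coders are masked to condition, masking to visit is not provided for, all three time points are coded from recordings, and 6.1 lists the baseline-to-virtual change with no arm contrast. If coders know the visit and inflate post-training scores by 0.1 to 0.3 SD, the nominal 5% within-arm error rate becomes about 8% to 29% at correlation 0.5, or 9% to 44% at 0.7. The inflation, the correlations and 24 per arm are assumptions.

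The between-arm contrast in 6.3.2, including maintenance, keeps its 5% error rate under a shift shared by both arms. The point is therefore worth correcting because correction is cheap, not because the randomised comparison has been shown to be unsound.

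In Cycle A the visit is visible on the recording (staff role play at baseline, officer at the end), so masking is not available and within-arm change there should not be read as efficacy.

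**What to change.** 1. In 9.1.2, for Cycle B, state that recordings are given random codes, stripped of visit and date, trimmed to the assessment scene, and scored in random order across subjects and visits, so that coders are masked to visit as well as condition. Score in batches, each only after its subjects have passed the 4-week visit.
2. In 6.1, in line with 6.3.2, state that Cycle B efficacy and maintenance rest on the contrast between VR and treatment-as-usual, and that within-arm change is descriptive. Say the same of within-arm change in Cycle A.

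The cost is relabelling and trimming files, keeping a random scoring list, and coding later than would otherwise be possible. No visit, sample size or participant burden changes. If the scene itself differs recognisably between visits, which the documents do not settle, masking will be partial, and the second change then carries most of the protection.
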